6.3. Lifestyle Restrictions

Per the Schedule of Activities (Section 2), qualified medical staff will provide diabetes management counseling, which will include instructions on diet and exercise and education about the signs, symptoms, and treatment of hypoglycemia, should it occur.

Patients should continue their usual exercise habits and generally follow a healthy meal plan (with consistent meal size and time of day) throughout the course of the study. Dietary counseling may be reviewed throughout the study, as needed. Per inclusion criterion [5] (Section 6.1), patients should not initiate during the study an organized diet and/or exercise weight reduction program other than the lifestyle and dietary measures for diabetes treatment.

Study participants should be instructed not to donate blood or blood products during the study.

6.4. Screen Failures

Individuals who do not meet the criteria for participation in this study (screen failure) must not be rescreened.

7. Treatments

7.1. Treatments Administered

Patients will be randomized in a 1:1:1:1 ratio to receive tirzepatide 5 mg, 10 mg, 15 mg, or insulin glargine. Tirzepatide will be administered QW as SC injection in patients with T2DM who are already treated with a stable dose of metformin alone or metformin plus a sulfonylurea.

Table GPHO.3 shows the randomized treatments for the entire treatment period.

The starting dose of tirzepatide will be 2.5 mg QW for 4 weeks, followed by an increase to 5 mg QW, for the duration of the study for the 5-mg group. For the 10-mg group, the starting dose of tirzepatide will be 2.5 mg QW for 4 weeks, then the dose will be increased by 2.5 mg every 4 weeks (2.5 to 5 to 7.5 to 10 mg) until the 10-mg dose is reached and maintained for the duration of the study. For the 15-mg group, the starting dose of tirzepatide will be 2.5 mg QW for 4 weeks, then the dose will be increased by 2.5 mg every 4 weeks (2.5 to 5 to 7.5 to 10 to 12.5 to 15 mg) until the 15-mg dose is reached and maintained for the duration of the study.

The starting dose of insulin glargine will be 6 IU/day at bedtime, titrated to a FBG between 72-100 mg/dL, following a TTT algorithm (Kawamori et al. 2008.). During the first 8 weeks, the insulin glargine dose adjustment will be determined by the investigator in discussion with the patient. From week 8 onwards, the decision of the titration will be made and implemented by the patient in a weekly manner. Between Week 8 and Week 16, investigators or study site personnel will contact the patient every 2 weeks (office or telephone visit) and will review the insulin dose adjustment made by the patient at each of these visits.

Table GPHO.3. Treatment Regimens

Name of Study Drug	Dosage	Frequency	Drug Formulation	Route of Administration
Tirzepatide	5 mg ^a	QW	Single-dose pen	SC
	10 mg ^a	QW	Single-dose pen	SC
	15 mg ^a	QW	Single-dose pen	SC
Insulin glargine	TTT dosing ^b	QD	prefilled pen	SC

Abbreviations: QD = once daily; QW = once weekly; SC = subcutaneous; TTT = treat-to-target.

^a The starting dose of tirzepatide will be 2.5 mg QW for 4 weeks, followed by an increase to 5 mg QW, for the duration of the study for the 5-mg group. For the 10-mg group, the starting dose of tirzepatide will be 2.5 mg QW for 4 weeks, then the dose will be increased by 2.5 mg every 4 weeks (2.5 to 5 to 7.5 to 10 mg) until the 10-mg dose is reached and maintained for the duration of the study. For the 15-mg group, the starting dose of tirzepatide will be 2.5 mg QW for 4 weeks, then the dose will be increased by 2.5 mg every 4 weeks (2.5 to 5 to 7.5 to 10 to 12.5-15 mg) until the 15-mg dose is reached and maintained for the duration of the study.

^b The starting dose of insulin glargine will be 6 IU/day ideally at bedtime, titrated to a FBG between 72-100 mg/dL, following a TTT algorithm. Insulin dose adjustments will be made in Study Period II per the TTT algorithm.

The investigator or his/her designee is responsible for the following:

- Explaining the correct use of study drugs to the patient or patient representative, and SDP or insulin glargine training. For the SDP a demonstration device will be used.
- Explaining the correct use of concomitant metformin, sulfonylurea (if used) to the patient, including any contraindications and appropriate dosing per country-specific labeling
- Verifying that instructions are followed properly
- Maintaining accurate records of investigational product dispensing and collection

Patients should return all study drugs to the site according to the Schedule of Activities (Section 2). Patients should be instructed to discard all used SDPs and insulin glargine pens in a closeable, puncture-resistant container according to local regulations.

7.1.1. Packaging and Labelling

The sponsor will provide tirzepatide in prefilled pens (SDP) and insulin glargine in prefilled pens. These will be dispensed via an interactive web-response system (IWRS). Single-dose pens and prefilled pens will be packaged in cartons to be dispensed. Clinical study materials will be labeled according to the country's regulatory requirements.

7.1.2. Medical Devices

The combination products provided for use in the study are tirzepatide investigational SDP and a marketed insulin glargine prefilled pen.

7.2. Method of Treatment Assignment

Patients who meet all criteria for enrollment will be randomized to 1 of the study treatment groups at Visit 3. Assignment to treatment groups will be determined by a computer-generated random sequence using an IWRS. Patients will be randomized in a 1:1:1:1 ratio to receive 5 mg tirzepatide, 10 mg tirzepatide, 15 mg tirzepatide, or insulin glargine.

7.2.1. Selection and Timing of Doses

7.2.1.1. Tirzepatide

Assignment to tirzepatide (3 doses) or insulin glargine will occur at randomization.

There are no restrictions on the time of day each weekly dose of tirzepatide is given, but it is advisable to administer the SC injections on the same day and same time each week. The actual date and time of all dose administrations will be recorded by the patient. If a dose of tirzepatide is missed, the patient should take it as soon as possible unless it is within 72 hours of the next dose, in which case, that dose should be skipped and the next dose should be taken at the appropriate time.

7.2.1.2. Insulin glargine

Patients in the insulin glargine group will start their insulin glargine treatment with a single SC injection of insulin glargine ideally at bedtime on the day of Visit 3. The initial dose of insulin glargine should be determined by the patient's average plasma-equivalent FBG concentration from the previous 2-4 days before Visit 3. The initial dose of insulin glargine will be 6 IU/day

for patients who have an average FBG concentration of ≥ 7.8 mmol/L (140 mg/dL). The initial dose of insulin glargine for patients with an average FBG concentration of < 7.8 mmol/L (< 140 mg/dL) may be reduced by 1-2 IU/day at the investigator's discretion. All subsequent glargine dose adjustments should be determined based on the algorithm in [Table GPHO.4](#).

Table GPHO.4. Dosing Titration Schedule for Once-Daily Insulin Glargine (TTT Algorithm)

Average of self-monitored plasma-equivalent FBG measurements from the previous 2-4 days	Change in insulin glargine dose (IU/day)
≥ 6.1 mmol/L (≥ 110 mg/dL)	+2
5.6 – 6.1 mmol/L (101 – 109 mg/dL)	+1 or +2 (at the investigator's discretion)
4.0 – 5.6 mmol/L (72 – 100 mg/dL)	No change in dosage
3.3 – 3.9 mmol/L (60 – 71 mg/dL)	-1
< 3.3 mmol/L (< 60 mg/dL)	-2

Notes: The FBG concentrations listed above refer to fasting plasma glucose concentrations obtained from a laboratory or FBG concentrations obtained using an International Federation of Clinical Chemistry (IFCC) plasma-equivalent BG meter. If only one prebreakfast SMBG value is available, the patient should contact the investigator site for instructions on adjusting insulin dose.

Source: Kawamori et al. 2008.

Regular FBG measurements are required during the study treatment period for the purpose of adjusting the dose of insulin glargine, if necessary, and monitoring patient safety. Patients should monitor their FBG concentrations using the plasma-equivalent BG meter provided to them for this study. During the first 8 weeks of treatment, patients should measure their prebreakfast FBG concentration every morning before any OAM have been taken and record the result in their study diary. From week 8 onwards, patients are recommended to measure and record their prebreakfast FBG concentration everyday, if considered appropriate by the investigator. During the first 8 weeks, the insulin glargine dose adjustment will be determined by the investigator in discussion with the patient. From week 8 onwards, the decision of the titration will be made and implemented by the patient in a weekly manner. The investigator and/or patients will titrate the dose of insulin glargine every week according to the patient's average FBG concentration for the previous 2-4 days. The target FBG range is between 4.0-5.6 mmol/L (72-100 mg/dL).

Patients should be instructed not to make up missing doses. If they forget to take their dose of insulin glargine on a particular day, they should record this in their patient diary and take their next dose as scheduled on the following day (that is, the dose is not doubled to make up for the missing dose on the previous day).

7.3. Blinding

This trial is an open-label study due to the differences in dosing schedule, titration, and devices between once-weekly tirzepatide and once-daily insulin glargine. It is not blinded between different doses of tirzepatide.

7.4. Dosage Modification

7.4.1. Study drugs

Details about dose administration of tirzepatide during the study are described in Sections 7.2.1 and 8.1.2. Insulin glargine will be adjusted according to the TTT algorithm (see Section 7.2.1.2).

7.4.2. Reduction and/or Discontinuation of Concomitant Antihyperglycemic Medications

After randomization, discontinuation of metformin or a sulfonylurea (if used) or change in dosage is not permitted, except in the following situations:

- 1) In the event of a hypoglycemic episode(s) (clinical symptoms of hypoglycemia and/or blood glucose (BG)-confirmed symptomatic hypoglycemia [glucose concentration ≤ 3.0 mmol/L {54mg/dL}]):
 - Patients in the tirzepatide groups on dual oral treatment of metformin and sulfonylurea may reduce/discontinue the dose of either metformin or sulfonylurea, but are recommended to reduce/discontinue the dose of sulfonylurea first. When hypoglycemia develops in patients on tirzepatide and metformin monotherapy, the dose of metformin may be reduced or discontinued.
 - Patients in the insulin glargine group must adjust the dose of insulin glargine following the TTT algorithm (section 7.2.1.2). In the event of recurrent hypoglycemic episodes despite reductions of the insulin dose, the investigator may consider a reduction in the dose of the OAMs. In that case, patients on dual oral treatment of metformin and sulfonylurea may reduce/discontinue the dose of either metformin or sulfonylurea, but are recommended to reduce/discontinue the dose of sulfonylurea first. If the patient is on metformin monotherapy, the dose of metformin may be reduced or discontinued.
- 2) In certain situations that require short-term discontinuation in line with the product(s) labeling for each respective country (for example: for metformin: severe dehydration, elective surgery, or need for radiologic exam involving IV iodinated contrast dye). Once the situation that led to temporary discontinuation of the drug resolved, treatment should be restarted at investigator discretion.
- 3) If a patient develops contraindications to metformin or sulfonylurea (if used), such that the use of the drug is contraindicated according to the country-specific label, the drug should be discontinued; in this case, the insulin glargine dose may need to be further adjusted.

A patient will be considered noncompliant with the protocol (protocol deviation) if he/she changes the dose or discontinues metformin or sulfonylurea (if used) for reasons other than those described here. In the case of noncompliance that lasts >14 days during the treatment period, the patient will not be included in the per-protocol (PP) analyses.

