- ^k Patient is required to collect two 7-point SMBGs on nonconsecutive days prior to the next visit. A 7-point SMBG consists of measurements before and 2 hours after each of 3 main meals within the same day and at bedtime. These SMBG profiles will be collected by the patient within 2 weeks prior to the assigned visits. If 7-point SMBG is not performed, then data from the most recent nonconsecutive 4-point SMBG (3 before each meal and one at bedtime) profiles can be used. If more than 2 SMBG profiles are available, the 2 most recent profiles on nonconsecutive days should be used. In the weeks that the 7-point profiles are performed, the 4-point SMBG profiles will not be needed.
- ^l Patients should administer their first dose of tirzepatide at the end of this visit, after all other study procedures and randomization.
- ^m During the first 8 weeks, the dose adjustment will be determined by the investigator in discussion with the patient by following a TTT algorithm. After Week 8, the dose adjustment will be determined by the patient in a weekly manner and will be reviewed by the investigator at each office visit. The dose adjustment will happen weekly during the first 16 weeks, and it is assumed that the dose will stay relatively stable from Week 16 onwards. Assessment of the patient's compliance to the TTT algorithm will be collected in the eCRF at Visits 7, 9, 11, 13, 15 and 19 for the period since the previous visit. PIs will be reminded that the review of dose is based on daily FBG.
- ⁿ A serum pregnancy test will be performed at Visit 1 for women of childbearing potential only. Females of childbearing potential are those who are not surgically sterilized and between menarche and 1-year postmenopausal.
- ^o A urine pregnancy test must be performed at Visit 3 with the result available prior to randomization and first injection of study drug(s) for women of childbearing potential only. Additional pregnancy tests will be performed at Visits 13, 17, and 19. Pregnancy tests may also be performed at the investigator's discretion during the study. If required per local regulations and/or institutional guidelines, pregnancy testing can also occur at other times during the study treatment period.

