Results of SMBG and hypoglycemic events will be used by the patient to assess insulin glargine doses per the TTT algorithm. Additional assessments may be requested by the investigator based on his/her clinical judgment. Outcome of the assessment will be recorded in patient diaries.

Compliance with the tirzepatide administration schedule and compliance with the insulin glargine TTT algorithm will be assessed at every office visit and collected in the eCRF at prespecified visits (Section 2). Based on the outcome of these reviews, the site staff should discuss additional insulin glargine dose adjustments while the patient is still at the site and provide retraining, if needed.

Patients should be instructed to contact the investigative site for assistance as soon as possible if they experience any difficulties administering their study medication or with the TTT algorithm at any time during the study treatment period. Patients should also be advised about the appropriate course of action in the event that study drug is not taken at the required time (late/missing doses).

Study Period III (safety follow-up period)

Safety follow-up (Visit 801) visits:

All patients who complete the treatment period are required to complete Visit 801, a safety follow-up visit approximately 4 weeks after their last dose. Patients discontinuing the study early and performing an early termination (ET) visit will also be asked to perform the safety follow-up visit, so that the safety follow-up visit will be their final visit. During the safety follow-up period, patients will not receive study drug. Patients may be treated with another glucose-lowering intervention decided upon by the investigator. Initiation of new antihyperglycemic therapy for the safety follow-up period will not be classified as “rescue therapy”. Prohibited anti-diabetes medications include GLP-1 receptor agonists, dipeptidyl peptidase (DPP-4) inhibitors, fixed-dose combination with component of GLP-1 receptor agonists or DPP-4 inhibitor, and pramlintide. Other basal insulin are also prohibited for patients assigned to insulin glargine. Patients are required to return any remaining study diaries to the study site at the end of this period.

Study Procedures

Patients will perform study procedures listed in the Schedule of Activities (Section 2).

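### After a hypoglycemic episode the written glargine titration table still calls for +1 or +2 IU whenever the fasting mean is 101 mg/dL or higher, because it has no hypoglycemia override

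*Protocol*

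**What the plan says.** Protocol 7.4.2 covers hypoglycemia, defined there as clinical symptoms and/or symptomatic hypoglycemia confirmed at 3.0 mmol/L (54 mg/dL) or lower. For the comparator arm it says: "Patients in the insulin glargine group must adjust the dose of insulin glargine following the TTT algorithm". It then allows oral agents to be reduced if episodes recur, in words that presume the insulin dose has already come down.

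The algorithm is in 7.2.1.2: "All subsequent glargine dose adjustments should be determined based on the algorithm in" Table GPHO.4. The basis is the "average FBG concentration for the previous 2-4 days". Neither the table nor its notes mention hypoglycemic events. The one note that sends a patient to the site concerns missing data: "If only one prebreakfast SMBG value is available, the patient should contact the investigator site for instructions on adjusting insulin dose".

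Three other statements bear on the point:
- Section 5.1 gives events a role: "Results of SMBG and hypoglycemic events will be used by the patient to assess insulin glargine doses per the TTT algorithm".
- Footnote m to the Schedule of Activities (Section 2) ties dose review to fasting values: "PIs will be reminded that the review of dose is based on daily FBG".
- Section 7.2.1.2 passes the decision to the patient: "From week 8 onwards, the decision of the titration will be made and implemented by the patient in a weekly manner".

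**The concern.** The 7.4.2 trigger is not limited to fasting readings, but the table sees only fasting readings, and only as a mean. A daytime or nocturnal episode may leave no trace in that mean, and a single low fasting value can be averaged away. If the patient's fasting mean is still above target, following the plan exactly means raising basal insulin at the first weekly adjustment after an episode.

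What is at stake is patient safety in the comparator arm. Hypoglycemia is also a planned comparison between arms (Protocol 10.3.4.1; SAP 6.13.2.1), without type 1 error control, and avoidable glargine events would count against the comparator there.

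**Working it through.** The plan states no figure to reproduce here. The check applies Table GPHO.4 as written.

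**Inputs (Table GPHO.4, mean fasting glucose in mg/dL):** below 60, -2 IU; 60-71, -1; 72-100, no change; 101-109, +1 or +2; 110 or higher, +2. In the 101-109 row the investigator's discretion is between two increases; zero is not offered.

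**Step 1. Episode that does not show in a fasting value.** The table's answer depends only on the fasting mean: 90 gives no change, 105 gives +1 or +2, and 130 gives +2.

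**Step 2. One fasting value of 54 among n values.** The mean reaches a threshold T when the other n-1 values average (nT - 54)/(n - 1).

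| n | Dose cut (mean below 72): others average below | Any increase (T = 101): others average at least | +2 IU (T = 110): others average at least |
|---|---|---|---|
| 2 | (144 - 54)/1 = 90 | (202 - 54)/1 = 148 | (220 - 54)/1 = 166 |
| 3 | (216 - 54)/2 = 81 | (303 - 54)/2 = 124.5 | (330 - 54)/2 = 138 |
| 4 | (288 - 54)/3 = 78 | (404 - 54)/3 = 116.7 | (440 - 54)/3 = 128.7 |

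An increase after a low fasting value therefore needs the other values to be well above the 72-100 target.

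**Step 3. How often, under assumptions.** The documents give no within-patient SD or event rate. The following assumes independent normal fasting values and counts any value of 54 or lower, whether or not it was symptomatic. It was simulated with at least 2,000,000 windows per setting.

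- Mid-target patient (mean 86, SD 14 to 27): given a window with such a value, the table gives an increase in under 2% of cases at every n.
- Above-target patient (mean 120): the share of all windows that contain such a value and still yield an increase is as follows.

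| SD | n = 2 | n = 3 | n = 4 |
|---|---|---|---|
| 14 | about 0 | about 0 | about 0 |
| 20 | 0.005% | 0.05% | 0.11% |
| 27 | 0.14% | 0.70% | 1.49% |

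At SD 27 such windows are themselves uncommon (1.4% to 2.9%). Given one, an increase follows in about 10%, 33% or 51% of cases (n = 2, 3, 4). The result is very sensitive to the SD. Events outside the fasting state are not in this model, and for them Step 1 applies directly.

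**Step 4. Where the decision sits.** To Week 8 the investigator decides with the patient. From Week 8 the patient decides weekly, with site contact every 2 weeks to Week 16. Scheduled visits then fall at Weeks 16, 20, 24, 32 and 40, so late in the study they are 8 weeks apart.

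**The case against.** The strongest reply is that nobody intended an increase. Section 7.4.2 mainly governs oral agents, its next sentence presumes reduced insulin, the table has -1 and -2 steps, and 5.1 names events as an input. That intent is visible, and a reader should not infer that the protocol means to raise insulin after hypoglycemia. But no section turns the intent into a dose step, and a patient adjusting alone has only the table.

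The safeguards are real. Section 9.2.2.1 requires each suspected or confirmed event to be categorized and its contributing factors established, with further education where appropriate. Events are collected at every visit, including telephone visits. Patients are trained in managing hypoglycemia, and are told to "contact the investigative site for assistance as soon as possible if they experience any difficulties administering their study medication or with the TTT algorithm". Extra calls and visits are allowed. Titration starts at 6 IU and moves weekly, and the dose is expected to be stable from Week 16. These lower the risk. None of them names a low reading as a reason to hold an increase or to call before the next one.

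Three stronger readings are tempting and are not supported:
- A reader might infer that no change is also wrong when the fasting mean is on target. The cause may be a meal, exercise or the sulfonylurea, and nothing in the documents shows that basal insulin must then be cut.
- A reader might infer that reducing an oral agent without a prior insulin cut would be a protocol deviation. Hypoglycemia is itself a listed reason for an oral-agent change, so this is not established.
- A reader might infer bias in the HbA1c or weight results. The documents give no basis for that.

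One objection shapes the remedy. Section 5.4 stresses optimal glargine titration. A hold triggered by unconfirmed symptoms in an open-label trial could under-titrate the comparator and favor tirzepatide on HbA1c. That stands, and the hold must be narrow.

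**Conclusion.** The point holds as a gap in a written dosing rule. Table GPHO.4, which 7.4.2 makes mandatory after hypoglycemia, calls for +1 or +2 IU whenever the fasting mean is 101 mg/dL or higher, and no text overrides it. This concerns mainly non-fasting events and above-target patients. Under the assumptions used, the fasting-value route accounts for between essentially none and about 1.5% of windows in an above-target patient. The frequency from non-fasting events cannot be derived, so no overall rate is claimed. Each weekly step is at most 2 IU.

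The conclusion rests on the protocol's table and text. The published algorithm that it cites and the patient training materials were not available, and either might contain an override. It is worth fixing as a low-cost patient-safety improvement.

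**What to change.** Add a rule to Table GPHO.4 and to the patient titration instructions, with cross-references from 5.1 and 7.4.2:

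- **Trigger:** since the last adjustment, a symptomatic episode confirmed at 3.0 mmol/L (54 mg/dL) or lower, or a severe episode as defined in 9.2.2.1.
- **Action:** the dose is not increased at the next weekly adjustment, whatever the mean fasting glucose, and the patient contacts the site. The investigator reviews the cause as 9.2.2.1 requires and decides whether to reduce. The sponsor sets the size of the step.
- **Limit:** the hold lasts one weekly cycle, after which titration by the table resumes. Unconfirmed symptoms alone do not trigger it.

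The cost is a short amendment, revised patient instructions and site retraining, with slightly slower glargine titration in the affected patients. It needs no new data and no additional patients.
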